7.1.3 FORMS FOR DATA COLLECTION

- Patient Consent Forms for AC paracentesis- *Trial I- at Exam 0 and Exam 2, trial II- during recurrence*
- Eligibility/screening form: Trial I-Exam 1 and Trial II-Exam 1
- Patient Consent Forms for clinical trial: Trial I-Exam 1 and Trial II-Exam 1 (for new participants)
- Baseline History Form: Trial I-Exam 1
- Clinical Eye Exam Form: All Exams in Trial I and Trial II
- Medication Log (to be completed by patient): Trial I- Exam 2, and 3, Trial II- Exam 2- 7
- Serious Adverse Event Narrative (if applicable): All Exams in Trial I and Trial II
- Patient Dropout Form (if applicable): Trial I- Exam 2, and 3, Trial II- Exam 2-7
- Protocol Deviation Form (if applicable): All Exams in Trial I and Trial II

7.2 Adverse Events and Serious Adverse Events

Adverse event means any untoward medical occurrence associated with the use of an intervention in humans, whether or not considered intervention-related (21 CFR 312.32 (a)).

An adverse event (AE) or suspected adverse reaction is considered "serious" if, in the view of either the investigator or sponsor, it results in any of the following outcomes: death, a life-threatening adverse event, inpatient hospitalization or prolongation of existing hospitalization, a persistent or significant incapacity or substantial disruption of the ability to conduct normal life functions, or a congenital anomaly/birth defect. Important medical events that may not result in death, be life-threatening, or require hospitalization may be considered serious when, based upon appropriate medical judgment, they may jeopardize the participant and may require medical or surgical intervention to prevent one of the outcomes listed in this definition.

7.2.1 NON-SERIOUS ADVERSE EVENTS

Non-serious adverse events may include any unfavorable medical occurrences in patients who have ever received study medication, regardless of any causal relationship with treatment. Examples may include:

1. Increased intraocular pressure (>24 mm Hg)
2. Abnormal lab findings (rise in creatinine to ≥ 1.5 to < 2 mg/dL, reduction of white blood cell count to below 2.5)
3. Concurrent accident or illness
4. Increase in the frequency and severity of symptoms of a pre-existing condition
5. Side effects intolerable to patient (gastrointestinal upset, nausea, vomiting, fatigue)
6. Signs of corneal or conjunctival toxicity (epitheliopathy, conjunctivitis)

7.2.2 DOSE REDUCTION DUE TO SAFETY

In the event of a non-serious adverse event in the form of a laboratory abnormality, dose reductions in study treatments should be made. This will entail decreasing the dose of valganciclovir to 450 mg PO BID. Topical drop frequency will be decreased to 3 times daily. In the event of a non-serious lab abnormality, repeat testing should be ordered at 7 days of treatment with the reduced dose in order to monitor for resolution.

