2.3 Risk/Benefit Assessment

2.3.1 KNOWN POTENTIAL RISKS

The Medication risks:

Patients randomized to receive oral valganciclovir will be at risk of developing complications due to systemic toxicity. Although this drug is widely prescribed to treat CMV anterior uveitis in the United States, there are known adverse effects. Common ones include fever, headache, insomnia, diarrhea, nausea, vomiting, and abdominal pain. Rare side effects include hematologic abnormalities, acute renal failure, infertility, teratogenesis, and carcinogenesis. Patients randomized to receive topical ganciclovir eye drops will be subjected to the risks of topical toxicity. These include corneal epitheliopathy and conjunctivitis, both of which are almost always reversible upon discontinuation of the topical medication.

Minimizing medication risks:

Due to the potential complications associated with oral valganciclovir, patients will obtain pre-study labs, as well as monitoring labs throughout the study. The pre-study labs are to ascertain whether an individual is at greater risk of developing complications such as bone marrow suppression or acute renal failure. Patients identified as being high risk will be excluded from the study, as specified in our protocol. Patients enrolled in the study will receive regular laboratory tests in order to monitor CBC and renal function. Those that develop blood or renal abnormalities as specified in the protocol will be removed from the study. For patients that are randomized to receive topical antiviral therapy, the regular schedule of follow-up with clinical exam by a study ophthalmologist will provide ample opportunity to detect topical toxicity and discontinue medications as described in our protocol.

Procedural risks:

Although extremely rare, risks associated with anterior chamber paracentesis include endophthalmitis and traumatic cataract, both of which can lead to vision loss. In rare cases, endophthalmitis warrants need for eye removal.

Minimizing procedural risk:

All study ophthalmologists are trained to safely utilize anterior chamber paracentesis techniques to access fluid in the anterior chamber. Sterilization drops will be used in order to minimize the risks of intra-ocular infection.

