4 STUDY DESIGN

4.1 Overall Design

The Systemic and topical antiviral control of cytomegalovirus anterior uveitis: treatment outcomes (STACCATO) study will enroll participants with PCR-proven CMV anterior uveitis into a sequential double-masked randomized clinical trial in the US and Asia. In Trial I, participants will be randomized to one of the three treatment groups:

Group 1: Valganciclovir tablets 900 mg PO BID (4 tablets daily) and Placebo drops 1 drop 6 times daily

Group 2: Topical ganciclovir 2% 1 drops 6 times daily and Placebo tablets 2 tablets PO BID (4 tablets daily)

Group 3: Placebo tablets 2 tablets PO BID (4 tablets daily) and Placebo drops 1 drop 6 times daily

After participants achieve control of their inflammation, they will enter Trial II at which point they will be re-randomized to one of the three arms in Trial I at a prophylactic dosing. Additionally, patients with known CMV anterior uveitis, but who are inactive, may enter Trial II directly. Recurrences of inflammation in Trial II will be assessed for presence of detectable viral load. Those who agree to participate will be randomized at baseline and after achieving clinical quiescence, get re-randomized to one of the three treatment groups:

Group 1: Valganciclovir tablets 450 mg PO BID (2 tablets daily) and Placebo drops 1 drop BID

Group 2: Topical ganciclovir 2% 1 drop BID and Placebo tablets 1 tablet PO BID (2 tablets daily)

Group 3: Placebo tablets 1 tablet PO BID (2 tablets daily) and Placebo drops 1 drop BID

All study ophthalmologists and participants will remain masked to treatment assignment after enrollment. Due to the treatment design, all participants will receive both pills and eye drops. An interim analysis will be performed for both trials once primary outcome data is available for one third of the patients.

4.1.1 . STUDY MASKING PROCEDURES (EXAM #2 AND 3)

- The patient comes for the study visit and meets with the study coordinator before seeing their study doctor. This will facilitate masking of ophthalmologists and participants. All outcome assessors including lab technicians for trial I and ophthalmologists for trial II will remain masked. To facilitate interim and safety analysis, a data team member may also be unmasked.
- The patient's medication bottles are immediately placed in a secure, black bag and left at the study coordinators desk for the remainder of the visit. Patient medication calendars should also be placed in the black bag.

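### Protocol 7.2.2's dose-reduction targets work only in Trial I, and patients who enter Trial II directly have no safety-lab criteria and no labs scheduled before randomisation

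*Protocol*

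**What the plan says.** **Dose reduction.** Protocol 7.2.2 says that after a non-serious laboratory abnormality "dose reductions in study treatments should be made". It then fixes the targets: "This will entail decreasing the dose of valganciclovir to 450 mg PO BID. Topical drop frequency will be decreased to 3 times daily". It adds that "repeat testing should be ordered at 7 days of treatment with the reduced dose". The section does not distinguish Trial I from Trial II, and neither document has another lab-triggered reduction rule. The non-serious laboratory examples in 7.2.1 are a creatinine of 1.5 to below 2 mg/dL and "reduction of white blood cell count to below 2.5".

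**Trial II regimen.** In Protocol 4.1 the oral arm of Trial II is "Group 1: Valganciclovir tablets 450 mg PO BID (2 tablets daily) and Placebo drops 1 drop BID". The topical and placebo arms have the same tablet and drop counts.

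**Stopping.** 7.2.3 sets the serious laboratory thresholds: creatinine of 2 mg/dL or more, leukocytes of 1,000 or fewer, platelets below 20,000, or hemoglobin below 6.5 g/dL. 7.2.4 stops all study drug at that tier and asks that visits continue where possible. Section 2.3.1 says: "Those that develop blood or renal abnormalities as specified in the protocol will be removed from the study".

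**Direct entry.** Protocol 4.1 and SAP 2.1 allow patients with established but quiet disease to go straight into Trial II. The Trial II lists in 5.1 and 5.2 cover only a past positive CMV test, inactive inflammation and two weeks off antivirals. The blood-count, renal, pregnancy/breastfeeding and contraception criteria stand in the Trial I lists alone.

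**The concern.** Section 2.3.1 names blood abnormalities, acute renal failure and teratogenesis among the risks of valganciclovir, and the protocol relies on laboratory screening, monitoring and dose reduction to limit them. In Trial II two of these three controls have a gap.

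First, a site that applies 7.2.2 as written to a Trial II participant with a moderately raised creatinine or low white count leaves the tablet dose where it was. The repeat test, meant to show whether the abnormality resolves on less drug, is then drawn on an unchanged oral dose. Any further action depends on how the site reads 2.3.1 or on individual judgment, so the same result could lead one site to continue at full dose and another to withdraw the participant. This is mainly a safety matter, but in a masked multi-country trial it also makes treatment inconsistent.

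Second, a direct entrant could be randomised and start valganciclovir with low counts, impaired renal function or an unrecognised pregnancy, because no listed criterion excludes these and no laboratory test is scheduled in time to find them.

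**Working it through.** No power or alpha figure is involved. The check compares the 7.2.2 targets with the assigned regimens, then the Trial II eligibility lists with the visit schedules.

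**Step 1. The rule against each regimen** (assigned doses from 4.1, targets from 7.2.2).

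| | Assigned | 7.2.2 target | Change |
|---|---|---|---|
| Trial I tablets | 2 × 900 = 1,800 mg/day | 2 × 450 = 900 mg/day | −900/1,800 = −50% |
| Trial I drops | 6/day | 3/day | −3/6 = −50% |
| Trial II tablets | 2 × 450 = 900 mg/day | 2 × 450 = 900 mg/day | 0% |
| Trial II drops | 2/day | 3/day | no decrease possible; target is above the assigned number |

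The rule does what it intends in Trial I and has no usable content in Trial II.

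**Step 2. The range left uncovered in Trial II.** The non-serious tier begins at a creatinine of 1.5 mg/dL and mandatory stopping begins at 2 mg/dL. For white cells the corresponding values are below 2.5 and 1,000 or fewer. I read 2.5 as thousands per microlitre, which is an assumption because 7.2.1 prints no unit. Between these values the stated steps are the 7.2.2 reduction, which changes nothing for tablets, and the 7-day repeat test.

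**Step 3. How long and how often.** The schema places Trial II Exams 2 to 8 at months 1, 3, 5, 7, 9, 11 and 12. Scheduled labs are therefore two months apart from month 1 to month 11. Twelve months is the maximum exposure, since participants leave at recurrence. The planned oral arm is 35 of 105.

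**Step 4. Direct entrants: criteria.** Of the three Trial II inclusion items in 5.1, none concerns blood counts, renal function, pregnancy, breastfeeding or contraception. The same holds for the three Trial II exclusion items in 5.2. SAP 5.2 refers back to the protocol and adds nothing.

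**Step 5. Direct entrants: labs before randomisation.** Four places agree that there are none:
- the laboratory row of the Schedule of Activities is blank at Trial II Exam 1;
- 7.1.1 begins Trial II labs at Exam 2;
- 7.1.2 ties the pre-randomisation blood and pregnancy tests to Exam 0, a Trial I visit;
- the schema lists only an eye examination and the start of treatment at Trial II Exam 1.

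This agreement makes a table-reading error unlikely. The first labs come at Exam 2, month 1.

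**Step 6. How many direct entrants.** Trial II is sized from Trial I completers: 117 × 0.90 = 105.3, taken as 105 = 3 × 35; then 105 × 0.80 = 84 = 3 × 28. The sizing budgets no direct entrants, although Protocol 5.3 makes roll-over voluntary. The number is therefore unknown. Those who do enter have a one-in-three chance of the oral arm.

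**The case against.** The protocol is not silent on Trial II safety. Its 450 mg twice daily is the dose the sponsor already considers a suitable reduction for this laboratory tier. The repeat test still applies. All drug stops at the serious tier, and an investigator need not wait for the listed thresholds, because important events "may be considered serious when, based upon appropriate medical judgment, they may jeopardize the participant" (7.2). Section 7.2.3 has an open category, 7.2.5 has a physician review reported symptoms, and 2.3.1 promises pre-study labs and exclusion of high-risk patients. Participants who roll over had labs at Trial I Exams 0, 2 and 3.

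All of this stands and lowers the risk. It does not supply a Trial II step for the non-serious tier. If the 2.3.1 removal sentence is read to cover that tier, it conflicts with 7.2.2, which keeps the participant on a lower dose. The 2.3.1 promise of exclusion points to criteria elsewhere in the protocol, and for direct entrants none are listed.

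A reader might go further in three ways that the documents do not support.
- That 7.2.2 tells Trial II sites to raise the drops to three a day. It does not: the section concerns reductions and says the frequency is to be decreased. The target simply does not fit.
- That nobody checks direct entrants at all. An eligibility form and consent are scheduled at Trial II Exam 1 (Schedule of Activities and 7.1.3). The form's content is not in the documents. What can be said is that no laboratory or pregnancy check is scheduled and no such criterion is listed.
- That the length of Trial II or the drug taken before the first labs measures harm. Participants exit at recurrence, and the documents tie neither quantity to a toxicity threshold.

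**Conclusion.** Both parts hold, as gaps in patient safety rather than in the primary estimates or power.

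(a) The 7.2.2 targets apply by their wording to both trials but reduce treatment only in Trial I. In Trial II the oral reduction is zero, so for up to 12 months the non-serious laboratory tier has no working step between the repeat test and stopping, beyond investigator judgment and the general removal text. The rule's failure concerns Trial II as a whole, with the drug risk in the oral arm (35 planned). The documents give no rate for these abnormalities, so the number affected cannot be estimated.

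(b) Direct entrants have no blood-count, renal, pregnancy/breastfeeding or contraception criterion, and no labs or pregnancy test scheduled before month 1. Their number is not stated and may be small. Roll-over participants are not affected by this part.

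The conclusion rests on the protocol and SAP alone. The eligibility form and the manual of procedures might contain more, but a safety criterion and a dose rule belong in the protocol. The gaps should be closed by amendment.

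**What to change.** - **7.2.2:** label the current targets as Trial I only. Add a Trial II rule, either a step-down below 450 mg twice daily and below twice-daily drops or a temporary hold. The sponsor's clinicians and medical monitor should choose it, and it should be applied identically to active and placebo in all three arms to preserve masking.
- **5.1 and 5.2:** apply the Trial I blood-count, renal, pregnancy/breastfeeding and contraception criteria to Trial II.
- **Schedule of Activities, 7.1.1 and 7.1.2:** add a blood count, chemistry panel and pregnancy test before Trial II randomisation for direct entrants.
- **2.3.1:** state which laboratory tier leads to stopping drug, and whether follow-up continues, so that it agrees with 7.2.2 and 7.2.4.

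The cost is one IRB-approved amendment across the sites, a step-down or hold that works within the double-dummy supply, and one routine panel per direct entrant. A few direct entrants may be screened out; the documents do not allow an estimate of how many.

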7.2.3 SERIOUS ADVERSE EVENT (SAE)

Serious adverse events include any medical occurrence that results in the following outcomes, or any other adverse event classified as severe*:

1. Cr \geq 2 mg/dL, leukocytes \leq 1,000/ L, platelets $<$ 20,000/ L, or hemoglobin $<$ 6.5 g/dL
2. Death
3. Non-elective surgery or hospitalization for any reason
4. Myocardial infarction or stroke
5. Corneal perforation
6. Life-threatening adverse drug experience or any life-threatening event
7. Persistent or significant disability or incapacity
8. Cancer
9. Seizure
10. Congenital anomaly/birth defect
11. Disability or permanent damage
12. Required intervention to prevent permanent impairment/damage

7.2.4 MEDICATION CESSATION

In the event of a serious adverse event, all study medications should be stopped and the medical monitor should be informed via a protocol deviation form. Further medical management will be at the discretion of the treating ophthalmologist and any consulting services. These patients should continue with scheduled study visits if possible.

7.2.5 ADVERSE EVENT REPORTING

Non-serious and serious adverse events will be noted at each study visit by the study coordinator while meeting with the patient at the beginning of each study visit. If there are any reported symptoms (not only severe symptoms), the study physician will review them with the patient while remaining masked to determine if any action is needed.

In case of a Serious Adverse Event (SAE), the Investigator needs to write a summary of the SAE and submit to the Medical Monitor ([name]; [contact]), and Principal Investigator ([name]; [contact]) within 24 hours of the SAE. Information recorded in this message will include the nature of the event, date of onset, date of resolution, date of notification to Medical Monitor, and action taken. The Medical Monitor will review and decide if the serious adverse event was related to the study drug and collect additional information if needed.

The Medical Monitor will determine two things:

- 1) Whether this is a true adverse event and
- 2) Whether this is likely related to the study drug.

If the investigator thinks the SAE is related to the study drug, he/she can stop the study medication anytime (including prior to investigation by the medical monitor).

Any significant study drug-related adverse events will be reported by the coordinating center to the FDA and CHR office as appropriate. The principal statistician will inform the DSMC of serious adverse events by arm every month.

Any complications will be reported within 24 hours to the Principal Investigator ([name], [contact]).

7.3 Unanticipated Problems

7.3.1 DEFINITION OF UNANTICIPATED PROBLEMS (UP)

The Office for Human Research Protections (OHRP) considers unanticipated problems involving risks to participants or others to include, in general, any incident, experience, or outcome that meets all of the following criteria:

- Unexpected in terms of nature, severity, or frequency given (a) the research procedures that are described in the protocol-related documents, such as the Institutional Review Board (IRB)-approved research protocol and informed consent document; and (b) the characteristics of the participant population being studied;
- Related or possibly related to participation in the research (“possibly related” means there is a reasonable possibility that the incident, experience, or outcome may have been caused by the procedures involved in the research); and
- Suggests that the research places participants or others at a greater risk of harm (including physical, psychological, economic, or social harm) than was previously known or recognized.

7.3.2 UNANTICIPATED PROBLEM REPORTING

The investigator will report unanticipated problems (UPs) to the reviewing Institutional Review Board (IRB) and to the Data Coordinating Center (DCC)/lead principal investigator (PI). The UP report will include the following information:

- Protocol identifying information: protocol title and number, PI’s name, and the IRB project number;
- A detailed description of the event, incident, experience, or outcome;
- An explanation of the basis for determining that the event, incident, experience, or outcome represents an UP.
- A description of any changes to the protocol or other corrective actions that have been taken or are proposed in response to the UP.

To satisfy the requirement for prompt reporting, UPs will be reported using the following timeline:

- UPs that are serious adverse events (SAEs) will be reported to the IRB and to the DCC/study sponsor within 7 days of the investigator becoming aware of the event.
- Any other UP will be reported to the IRB and to the DCC/study sponsor within 30 days of the investigator becoming aware of the problem.
- All UPs should be reported to appropriate institutional officials (as required by an institution’s written reporting procedures), the supporting agency head (or designee),

and the Office for Human Research Protections (OHRP) within 30 days of the IRB's receipt of the report of the problem from the investigator.]

7.3.3 REPORTING UNANTICIPATED PROBLEMS TO PARTICIPANTS

Participants will be notified of UPs in aggregate. When UPs affect an individual, they will be notified individually by the treating physician.

8 STATISTICAL CONSIDERATIONS

8.1 Statistical Hypotheses

Specific Aim 1 (Trial I): To compare CMV viral load and inflammation after randomization to 7 days of oral valganciclovir, topical ganciclovir 2%, or placebo.

1a: We hypothesize that participants randomized to oral valganciclovir will have a lower viral load after 7 days compared to those randomized to either topical ganciclovir 2% or placebo (Trial I primary outcome).

1b: We hypothesize that a greater proportion of participants randomized to oral valganciclovir will have controlled inflammation compared to those randomized to either topical ganciclovir 2% or placebo.

Specific Aim 2 (Trial II): To compare the effect of long-term antiviral suppression on recurrence rate of inflammation.

2a: We hypothesize that participants randomized to placebo will have fewer recurrences over 12 months compared to those randomized to either oral valganciclovir or topical ganciclovir 2% (Trial II primary outcome).

2b: We hypothesize that aqueous obtained at the time of a recurrence of inflammation will demonstrate a detectable viral load and will correlate with level of inflammation.

Specific Aim 3 (samples from Trials I and II): To characterize host transcriptional signatures and viral genomic features in CMV anterior uveitis using RNA sequencing of aqueous samples.

3a: We hypothesize participants completing both trials who exhibit recurrent inflammation after antiviral suppression (Trial II) will have a higher prevalence of CMV mutations associated with antiviral resistance compared to baseline samples (Trial I).

3b: We hypothesize that host transcriptional profiles will (i) distinguish CMV anterior uveitis from anterior uveitis cases negative for CMV and unable to enter Trial I, (ii) we will identify non-CMV pathogens in cases unable to enter Trial I, and (iii) identify unique signatures associated with recurrent inflammation in Trial II participants.

Primary Outcome:

- Viral load after 7 days of treatment (Trial I)
- Recurrence of inflammation over 12 months (Trial II)

Secondary outcomes:

- Anterior chamber cell (Trials I and II)
- Intraocular pressure (Trials I and II)
- Visual acuity (Trials I and II)
- Corneal endothelial cell count and morphology (Trials I and II)
- Number of glaucoma medications (ocular hypertensive medication) (Trials I and II)
- Prevalence of mutations conferring antiviral resistance (Trials I and II)

